16.6 Results Reporting

16.6.1 Results Reporting on ClinicalTrials.gov: At study activation, this study will have been registered within the “ClinicalTrials.gov” website. The Primary and Secondary Endpoints along with other required information for this study will be reported on [REDACTED] For purposes of timing of the Results Reporting, the initial estimated completion date for the Primary Endpoint of this study is 3.25 years after the study opens to accrual. The definition of “Primary Endpoint Completion Date” (PECD) for this study is at the time the last patient registered has been followed for at least 6 months.

16.6.2 Publications: This study includes endpoints that require various amounts of follow-up. Due to this, primary endpoint results will be reported after all patients have completed the 6-month response assessment (6-12 months after completion of accrual). Time to event endpoints including PFS, TTNT, and TTC will require additional follow-up. These measures may be reported in the initial report with the CR rate, as well as after 3 years, 5 years, and 10 years after the completion of accrual.

16.7 Inclusion of Women and Minorities

16.7.1 This study will be available to all eligible patients, regardless of race, gender, or ethnic origin.

16.7.2 There is no information currently available regarding differential effects of this regimen in subsets defined by race, gender, or ethnicity, and there is no reason to expect such differences to exist. Therefore, although the planned analysis will, as always, look for differences in treatment effect based on racial and gender groupings, the sample size is not increased in order to provide additional power for subset analyses.

16.83 The geographical region served by MCCC has a population which includes approximately 5% minorities. Based on prior MCCC studies involving similar disease sites, we expect about 5% of patients will be classified as minorities by race and about 45% of patients will be women. Expected sizes of racial by gender subsets are shown in the following table:

Accrual Estimates by Gender/Ethnicity/Race for All Phase 2 and 3 Studies

Ethnic Category	Sex/Gender			
	Females	Males	Unknown	Total
Hispanic or Latino	1	1	0	2
Not Hispanic or Latino	57	69	0	126
Unknown	0	0	0	0
Ethnic Category: Total of all subjects	58	70	0	128
Racial Category				
American Indian or Alaskan Native	0	0	0	0
Asian	0	0	0	0
Black or African American	2	2	0	4
Native Hawaiian or other Pacific Islander	0	0	0	0
White	56	68	0	124
More than one race	0	0	0	0
Unknown	0	0	0	0
Racial Category: Total of all subjects	58	70	0	128

Ethnic Categories: **Hispanic or Latino** – a person of Cuban, Mexican, Puerto Rico, South or Central American, or other Spanish culture or origin, regardless of race. The term “Spanish origin” can also be used in addition to “Hispanic or Latino.”
Not Hispanic or Latino

Racial Categories: **American Indian or Alaskan Native** – a person having origins in any of the original peoples of North, Central, or South America, and who maintains tribal affiliations or community attachment.

Asian – a person having origins in any of the original peoples of the Far East, Southeast Asia, or the Indian subcontinent including, for example, Cambodia, China, India, Japan, Korea, Malaysia, Pakistan, the Philippine Islands, Thailand, and Vietnam. (Note: Individuals from the Philippine Islands have been recorded as Pacific Islanders in previous data collection strategies.)

Black or African American – a person having origins in any of the black racial groups of Africa. Terms such as “Haitian” or “Negro” can be used in addition to “Black or African American.”

Native Hawaiian or other Pacific Islander – a person having origins in any of the original peoples of Hawaii, Guam, Samoa, or other Pacific Islands.

White – a person having origins in any of the original peoples of Europe, the Middle East, or North Africa.

17.0 Pathology Considerations/Tissue Biospecimens

17.1 Summary Table of Research Tissue Specimens to be Collected for this Protocol

Correlative Study (Section for more information)	Mandatory or Optional	Type of Tissue to Collect	Block, Slides, Core, etc. (# of each to submit)	Visit 1 (Screening)	Process at site? (Yes or No)	Temperatu re Conditions for Storage /Shipping
Central Path review	Mandatory	H&E stained slides	H&E stained diagnostic slides	X	No	Ambient air
Tregs, Monocytes (Section 17.31)	Optional	Paraffin embedded	1 paraffin- embedded block; if block not available then 1 H&E slide and 20 (4 μ) unstained slides	X	No	Ambient air
Bcl-2 mutations (Section 17.31)	Optional	Paraffin embedded	1 paraffin- embedded block; if block not available then 1 H&E slide and 20 (4 μ) unstained slides	X	No	Ambient air
Research Fresh Tissue	Optional for patients enrolled at Mayo only	Fresh	Excisional or core needle (3-6 cores) biopsy	X	No	

17.2 Diagnostic Slides from Original and /or Recurrent Tissue

Central pathology review will be conducted for confirmation of diagnosis by [REDACTED] and colleagues at Mayo Clinic Rochester.

The appropriate representative tumor tissue samples will be forwarded to the Lymphoma SPORE Biospecimens Core for central diagnostic review and classification to confirm the diagnosis. This is a retrospective review to determine the evaluability of the patient's data for analysis. The results of the review are the purposes of the trial only and will not be returned to the site.

Required materials [REDACTED] ():

- Lymphoma Pathology Reporting Form (Complete Section I only)
- Bone marrow biopsy report
- Tumor tissue pathology report
- Tumor tissue diagnostic H&E stained slide
- Tumor tissue immunochemistry or immunophenotyping by flow cytometry report (if available)

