- 6.9a Treatment on this protocol must commence at the University of Iowa Holden Comprehensive Cancer Center or the Mayo Clinic Cancer Center under the supervision of a physician investigator registered with NCI Pharmaceutical Management Branch (PMB) and the Lymphoma SPORE Operations Office.
- 6.9b Blood draw kit is available on site.
- 6.9c Patient questionnaire booklet is available on site.

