7.2 Treatment Schedule – Arm B: Zevalin

Agent	Dose	Route	Day	Cycle Length
Rituximab ¹	250 mg/m ² /day	IV	1, 8	3 months
Zevalin	0.3 mCi/kg or 0.4 mCi/kg**	IV	8*	

- * Administer within 4 hours of completion of rituximab infusion.
- ** Maximum dose = 32 mCi. Dose at 0.4 mCi/kg for patients with platelet counts greater than or equal to 150,000/mm³ and at 0.3 mCi/kg for patients with platelet counts 100,000 to 149,000/mm³
- 1. Substitution of a rituximab biosimilar covered by patients' insurance plan is not allowed for Arm B.

The following pre-medications are suggested prior to rituximab: acetaminophen 650-1000 mg PO 30 minutes prior to rituximab and every 4 hours as needed for infusion related reactions (maximum of 4000 mg in 24 hours), diphenhydramine 50 mg PO 30 minutes prior to rituximab, diphenhydramine 25 mg IV every 4 hours as needed for infusion related reactions, meperidine 25 mg IV push as needed for rigors, may repeat x 1 dose if first dose is ineffective.

- 7.3 For this protocol, patients randomized to Zevalin can be treated either at the enrolling site or referred to Mayo Clinic Rochester, Arizona, or Florida for the Day 1, 8 rituximab and Zevalin on Day 8. The enrolling site is also permitted to provide Day 1 rituximab if this is prearranged and coordinated with the Zevalin site. This can be arranged by calling the study [REDACTED] after the patient has been registered.

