13.0 Treatment/Follow-up Decision at Evaluation of Patient

13.1 Patients will be evaluated per the test schedule during cycle 1 of treatment.

13.2 After treatment, patients will be observed at 3, 6, 9, 12, 18, 24, 30, 36, 48, and 60 months from day 1 of treatment.

13.3 Criteria for removing patients from treatment and initiating observation.

13.3.1 Requested withdrawal or patient non-compliance.

13.4 Patients who have progressive or relapsed disease, receive subsequent treatment for lymphoma, refuse further observation, or fail to return for evaluation during observation will go to event monitoring.

13.5 At 5 years from day 1 of treatment, all patients still on observation will go to event monitoring every 12 months until 10 years from time of registration per Section 18.0.

13.6 A patient is deemed *ineligible* if after registration, it is determined that at the time of registration, the patient did not satisfy each and every eligibility criteria for study entry.

The patient may continue protocol treatment at the discretion of the physician as long as there are no safety concerns, and the patient was properly registered. The patient will continue treatment (if no safety concerns), observation, and event monitoring as specified for all patients (or will be taken off study, if applicable).

- If the patient received treatment, the patient will continue treatment (if no safety concerns), observation, and event monitoring as specified for all patients.
- If the patient never received treatment, On-study material and the End of Active Treatment/Cancel Notification Form must be submitted. No further data submission is necessary.

13.7 A patient is deemed a *major violation*, if protocol requirements regarding treatment in cycle 1 of the initial therapy are severely violated that evaluability for primary end point is questionable. The patient may continue protocol treatment at the discretion of the physician as long as there are no safety concerns, and the patient was properly registered. The patient will continue treatment (if no safety concerns), observation, and event monitoring as specified for all patients.

13.8 A patient is deemed a *cancel* if he/she is removed from the study for any reason before any study treatment is given. On-study material and the End of Active Treatment/Cancel Notification Form must be submitted. No further data submission is necessary.

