18.0 Records and Data Collection Procedures

18.1 Submission Timetable

Initial Material(s)

Case Report Form (CRF)	Active-Monitoring Phase (Compliance with Test Schedule Section 4.0)
On-Study	≤14 days after registration
Adverse Event– Baseline	
Measurement – Baseline	
Tumor Tissue Biopsy Pathology Report	
CT/PET/MRI Scan Report	
Research Paraffin Embedded Submission – Baseline (All Patients)	≤30 days after registration
Research Fresh Tissue Submission – Baseline (Mayo Patients only)	
Research Blood Submission	≤ 21 days after registration
End of Active Treatment/Cancel Notification	Submit ≤14 days after registration if withdrawal/refusal occurs prior to beginning protocol therapy
Patient Questionnaire Booklet	≤14 days after registration - Patient questionnaire booklet must be used; copies are not acceptable for this submission.
Booklet Compliance	≤14 days after registration - This form must be completed only if the patient questionnaire booklet contains absolutely NO patient provided assessment information.

Central Pathology Review Material(s)

CRF	Active-Monitoring Phase (Compliance with Test Schedule Section 4.0)
Pathology Materials (this is for central review, eligibility, etc.)	Submit ≤30 days after registration (see Section 17.0)

Test Schedule Material(s)

CRF	Active-Monitoring Phase (Compliance with Test Schedule Section 4.0)		
	At each evaluation during treatment	At end of treatment	Observation
Evaluation/Treatment	X ²	X	

CRF	Active-Monitoring Phase (Compliance with Test Schedule Section 4.0)		
	At each evaluation during treatment	At end of treatment	Observation
Evaluation/Observation			X ¹
Nadir/Adverse Event (Cycles 1 & 2 Only)	X	X	X ³
Measurement	X	X	X
Research Blood Submission			X (see Section 14.0)
Patient Questionnaire Booklet ⁴	X	X	X
Booklet Compliance ⁵	X	X	X
End of Active Treatment/Cancel Notification		X	
ADR/AER	At each occurrence (see Section 10.0)		At each occurrence (see Section 10.0) ³
CT/PET/MRI Scan Report	X ⁶		X ⁶

1. Complete at each evaluation during Observation (see Section 4.0).
2. Complete at each evaluation during Active Treatment (see Section 4.0).
3. AE form and expedited reports needed for Cycle 1 (treatment – months 0-3) and Cycle 2 (first cycle of observation – months 3-6) only.
4. Patient questionnaire booklet **must** be used; copies are not acceptable for this submission.

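### Section 17.2 keeps central pathology results from the site, with no visible exception when the review finds a diagnosis other than follicular lymphoma grade I or II

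*Combined protocol and SAP*

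**What the plan says.** Section 4.0, footnote 8, allows registration on local pathology and sends every case to central review. Eligibility requires follicular lymphoma grade I or II (3.12); grades IIIA and IIIB are excluded (3.29g).

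Section 17.2 gives the purpose of the central review: "This is a retrospective review to determine the evaluability of the" patient's data. It then states: "The results of the review are the purposes of the trial only and will not be returned to the site". Section 18.1 lists the slides as "Pathology Materials (this is for central review, eligibility, etc", due within 30 days of registration. Treatment must start within 21 days of registration (6.6).

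Section 13.6 deals with patients found ineligible after registration: "The patient may continue protocol treatment at the discretion of the physician as long as there are no safety concerns". For those already treated it adds: "If the patient received treatment, the patient will continue treatment (if no safety concerns), observation, and event monitoring as specified for all patients". Section 13.2 sets the visits: "After treatment, patients will be observed at 3, 6, 9, 12, 18, 24, 30, 36, 48, and 60 months from day 1 of treatment".

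On location, 6.9a says "Treatment on this protocol must commence at the University of Iowa Holden Comprehensive Cancer Center or the Mayo Clinic Cancer Center", and the central review is done at Mayo Clinic Rochester (17.2). Section 7.3 says "patients randomized to Zevalin can be treated either at the enrolling site or referred to Mayo Clinic Rochester, Arizona, or Florida".

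**The concern.** The trial obtains a second reading of every patient's tumor and may act on it by declaring the patient ineligible or not evaluable. Under 17.2 as written, the physician caring for that patient does not receive the reading. If it points to grade III disease or to another lymphoma, the physician could go on observing the patient under a diagnosis that the trial itself has reason to question.

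What is at stake is individual care, mostly during follow-up. The comparison of complete response rates is not threatened.

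**Working it through.** The plan gives no figure to reproduce on this point. The check has three parts.

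**1. The provisions side by side**

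| Step | Provision | What it implies |
|---|---|---|
| Registration | 4.0, footnote 8 | Local diagnosis is enough |
| Central review | 17.2, 18.1 | Bears on evaluability and eligibility |
| Return of result | 17.2 | None, with no visible exception |
| Patient found ineligible | 13.6 | Physician judges safety and continuation |
| Return of genetic results | 14.4 | Ethics board route if clinically relevant; genetic tests only |

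When central pathology is the reason for ineligibility, 13.6 works only if the physician learns something of the result. Section 17.2 says the result is not sent. The two sections therefore conflict. Even bare notice of ineligibility would not carry the diagnosis needed to judge safety.

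**2. Where the review falls in the schedule**

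Let treatment start on day s after registration, with s = 0 to 21 (6.6). Slides are due by day 30 (18.1). Dosing is assumed to be on schedule.

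- Arm B (7.2): the last dose is on day s + 7, at most day 28. No dose remains after day 30.
- Arm A (7.1): doses are on days s, s + 7, s + 14 and s + 21. After day 30 there remain 0 doses if s is 0 to 9, 1 if s is 10 to 16, and 2 if s is 17 to 21. The last possible dose is on day 42.
- Month-3 visit, taken as 91 days: s + 91 − 30 = 61 to 82 days after the slide deadline. With the 1-week window (4.0, footnote 11), 54 to 89 days.
- Month-6 scan, the first scheduled after treatment, taken as 183 days: s + 183 − 30 = 153 to 174 days. With the window, 146 to 181 days.
- Scheduled scans at months 6, 12, 24, 36, 48 and 60 have gaps of 6, 12, 12, 12 and 12 months. Visits at months 18 and 30 fall between scans.
- Arm B also has blood counts in weeks 5 to 7 after Zevalin.

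These intervals run from a submission deadline. No turnaround for the review is stated; any turnaround shortens the time left to the next visit or scan.

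**3. What notification could do to the analyses**

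Sections 16.11 and 16.34 limit the primary analysis and the adverse event rates to eligible patients. A patient made ineligible by central review is already outside both. The sensitivity analysis in 16.11 keeps all treated patients, and anyone without a month-6 complete response counts as a non-responder. Assume 58 (116/2) to 64 (128/2) treated per arm. Each patient who leaves before month 6 and would otherwise have been a complete responder lowers that arm's rate by 1/64 = 1.6 to 1/58 = 1.7 percentage points.

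**The case against.** The strongest reply is that this is a deliberate separation. The review is retrospective and serves data classification, and the local pathologist remains responsible for the clinical diagnosis. That is a good reason not to return routine concordant results. It does not explain withholding a discordant one.

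A second reply is that 13.6 makes no sense unless the physician is told, so notification must happen in practice. The implication is fair, and the documents do not show that sites are left uninformed. But the step is unwritten, and 17.2 says the opposite.

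Third, the consent pages and the Lymphoma Pathology Reporting Form are not in the documents and might cover the case. That limit stands. If they do, the remedy is a cross-reference.

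Fourth, reviewing and treating institutions may coincide for some patients (6.9a, 17.2). The share is not given, Iowa is a separate institution, and 17.2 draws no distinction.

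A reader might also infer that a discordant central reading overturns the local diagnosis. The documents do not support this. Section 17.2 calls for a diagnostic H&E slide and reports, with immunophenotyping only where it exists, and gives the reading authority over evaluability. It raises a question about the local diagnosis and does not settle it. Nor would an inadequate or unreadable slide be evidence against that diagnosis.

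**Conclusion.** The point stands as a modest gap in patient safety. The visible text has a flat rule against returning central results, no exception for a different diagnosis, and a conflict with 13.6.

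The number of patients affected is unknown, because the documents give no discordance rate. The effect on treatment is small: at the slide deadline Arm B has no doses left and Arm A has 0 to 2 of 4. The exposure is mainly in follow-up, and it is tempered. Patients are low-burden candidates for observation (3.14, 3.17), visits and scans continue, and nothing prevents re-biopsy or treatment. A reader might take the intervals above as a measured delay in care. They describe the visit calendar, not a harm that has been quantified.

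The trial's main result is unaffected. This rests on the assumption that a discordant central finding is classed as ineligibility, as 18.1 suggests. The conclusion is limited to the visible text.

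**What to change.** Amend 17.2 along these lines: *Concordant results will not be returned. If central review of adequate material finds a diagnosis other than follicular lymphoma grade I or II, the finding will be sent to the enrolling investigator when the review is completed, for local re-review and application of 13.6.*

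State that inadequate or unreadable slides do not trigger notice of a discordant diagnosis. Apply the same rule in both arms and leave the analysis populations in 16.11 as they are.

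The cost is a short amendment, a notification step for discordant cases, and local re-review of those cases. Central review is already done on every patient, so it needs no extra reader or tissue. The downside is that some notified patients may leave protocol follow-up early. The effect of that is confined to the small shift in the sensitivity analysis shown above and some loss of later follow-up on patients already outside the primary analysis.

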17.3 Correlative Tissue Collection

17.31 Paraffin Embedded Tissue

17.311 Representative diagnostic FFPE tumor tissue block. If block cannot be sent then please send one (1) H&E slide, and twenty (20) 4 μ m unstained air-dried slides. Do not coverslip the unstained slides. If questions please [REDACTED]

18.0 Records and Data Collection Procedures

18.1 Submission Timetable

Initial Material(s)

Case Report Form (CRF)	Active-Monitoring Phase (Compliance with Test Schedule Section 4.0)
On-Study	≤14 days after registration
Adverse Event– Baseline	
Measurement – Baseline	
Tumor Tissue Biopsy Pathology Report	
CT/PET/MRI Scan Report	
Research Paraffin Embedded Submission – Baseline (All Patients)	≤30 days after registration
Research Fresh Tissue Submission – Baseline (Mayo Patients only)	
Research Blood Submission	≤ 21 days after registration
End of Active Treatment/Cancel Notification	Submit ≤14 days after registration if withdrawal/refusal occurs prior to beginning protocol therapy
Patient Questionnaire Booklet	≤14 days after registration - Patient questionnaire booklet must be used; copies are not acceptable for this submission.
Booklet Compliance	≤14 days after registration - This form must be completed only if the patient questionnaire booklet contains absolutely NO patient provided assessment information.

Central Pathology Review Material(s)

CRF	Active-Monitoring Phase (Compliance with Test Schedule Section 4.0)
Pathology Materials (this is for central review, eligibility, etc.)	Submit ≤30 days after registration (see Section 17.0)

Test Schedule Material(s)

CRF	Active-Monitoring Phase (Compliance with Test Schedule Section 4.0)		
	At each evaluation during treatment	At end of treatment	Observation
Evaluation/Treatment	X ²	X	

CRF	Active-Monitoring Phase (Compliance with Test Schedule Section 4.0)		
	At each evaluation during treatment	At end of treatment	Observation
Evaluation/Observation			X ¹
Nadir/Adverse Event (Cycles 1 & 2 Only)	X	X	X ³
Measurement	X	X	X
Research Blood Submission			X (see Section 14.0)
Patient Questionnaire Booklet ⁴	X	X	X
Booklet Compliance ⁵	X	X	X
End of Active Treatment/Cancel Notification		X	
ADR/AER	At each occurrence (see Section 10.0)		At each occurrence (see Section 10.0) ³
CT/PET/MRI Scan Report	X ⁶		X ⁶

1. Complete at each evaluation during Observation (see Section 4.0).
2. Complete at each evaluation during Active Treatment (see Section 4.0).
3. AE form and expedited reports needed for Cycle 1 (treatment – months 0-3) and Cycle 2 (first cycle of observation – months 3-6) only.
4. Patient questionnaire booklet **must** be used; copies are not acceptable for this submission.
5. This form must be completed **only** if the patient questionnaire booklet contains absolutely **NO** patient provided assessment information.
6. Submit copy of documentation of response or progression to the Lymphoma SPORE Operations Office, Attention: QAS for LS138D.

Follow-up Material(s)

CRF	Event Monitoring Phase ¹				
	q. 12 months until PD ²	At PD ²	After PD q. 12 mos.	Death	New Primary
Event Monitoring	X	X	X	X	At each occurrence

1. If a patient is still alive 10 years after registration, no further follow-up is required.
2. Submit copy of documentation of response or progression to the MCCC Operations Office, Attention: QAS for LS138D.

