10.0 Adverse Event (AE) Reporting and Monitoring

10.1 Adverse Event Characteristics

CTCAE term (AE description) and grade: The descriptions and grading scales found in the revised NCI Common Terminology Criteria for Adverse Events (CTCAE) version 4.0 will be utilized for AE reporting. All appropriate treatment areas should have access to a copy of the CTCAE version 4.0. A copy of the CTCAE version 4.0 can be downloaded from the CTEP web site:

(http://ctep.cancer.gov/protocolDevelopment/electronic_applications/ctc.htm)

10.11 Adverse event monitoring and reporting is a routine part of every clinical trial. First, identify and grade the severity of the event using the CTCAE version 4.0. Next, determine whether the event is expected or unexpected (see Section 10.2) and if the adverse event is related to the medical treatment or procedure (see Section 10.3). With this information, determine whether the event must be reported as an expedited report (see Section 10.4). **Important:** Expedited adverse event reporting requires submission of a MedWatch report(s). Expedited reports are to be completed within the timeframes and via the mechanisms specified in Sections 10.4. All AEs reported via expedited mechanisms must also be reported via the routine data reporting mechanisms defined by the protocol (see Sections 10.52 and 18.0).

10.12 Each CTCAE term in the current version is a unique representation of a specific event used for medical documentation and scientific analysis and is a single MedDRA Lowest Level Term (LLT). Grade is an essential element of the Guidelines and, in general, relates to **severity** for the purposes of regulatory reporting to NCI.

NOTE: A severe AE, as defined by the above grading scale, is **NOT** the same as serious AE which is defined in the table in Section 10.4.

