10.41 Special Situations for Expedited Reporting

EXPECTED Serious Adverse Events

An expedited report may not be required for specific Grade 1, 2, 3 and 4 Serious Adverse Events where the AE is **EXPECTED**. Any protocol specific reporting procedures MUST BE SPECIFIED BELOW and will supercede the standard Expedited Adverse Event Reporting Requirements. Note: These adverse events must still be reported through the routine reporting mechanism [i.e. Nadir/Adverse Events Form]; see footnote 1.

System Organ Class (SOC)	Adverse event/ Symptoms	CTCAE Grade at which the event will not be expeditedly reported. ¹
Blood and lymphatic system disorders	Anemia	≤ Grade 4
Investigations	White blood cell decreased	≤ Grade 4
	Lymphocyte count decreased	≤ Grade 4
	Neutrophil count decreased	≤ Grade 4
	Platelet count decreased	≤ Grade 4

¹ These exceptions only apply if the adverse event does not result in hospitalization. If the adverse event results in hospitalization, then the standard expedited adverse events reporting requirements must be followed.

Specific protocol exceptions to expedited reporting should be reported expeditiously by investigators **ONLY** if they exceed the expected grade of the event.

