10.53 Secondary Malignancy

- A **secondary malignancy** is a cancer caused by treatment for a previous malignancy (e.g., treatment with investigational agent/intervention, radiation or chemotherapy). A secondary malignancy is not considered a metastasis of the initial neoplasm.
- All secondary malignancies that occur following treatment with an agent under an IND/IDE be reported. Three options are available to describe the event:
 - Leukemia secondary to oncology chemotherapy (e.g., Acute Myelocytic Leukemia [AML])
 - Myelodysplastic syndrome (MDS)
 - Treatment-related secondary malignancy
- Any malignancy possibly related to cancer treatment (including AML/MDS) should also be reported via the routine reporting mechanisms outlined in each protocol.

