10.6 Required Routine Reporting

Adverse events to be graded at each evaluation and pretreatment symptoms/conditions to be evaluated at baseline per the CTCAE v4.0 grading unless otherwise stated in the table below:

System Organ Class (SOC)	Adverse event/Symptoms	Baseline	Each evaluation
Investigations	Neutrophil count decreased	X	X
	Platelet count decreased	X	X
	White blood cell decreased	X	X
Skin and subcutaneous tissue disorders	Rash maculo-papular	X	X

10.61 Submit via appropriate MCCC Case Report Forms (i.e., paper or electronic, as applicable) the following AEs experienced by a patient and not specified in Section 10.6

10.611 Grade 2 AEs deemed *possibly, probably, or definitely* related to the study treatment or procedure.

10.612 Grade 3 and 4 AEs regardless of attribution to the study treatment or procedure.

10.613 Grade 5 AEs (Deaths)

10.6131 Any death within 30 days of the patient's last study treatment or procedure regardless of attribution to the study treatment or procedure.

10.6132 Any death more than 30 days after the patient's last study treatment or procedure that is felt to be at least possibly treatment related must also be submitted as a Grade 5 AE, with a CTCAE type and attribution assigned.

10.62 Refer to the instructions in the Forms Packet (or electronic data entry screens, as applicable) regarding the submission of late occurring AEs following completion of the Active Monitoring Phase (i.e., compliance with Test Schedule in Section 4.0).

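### Section 18.1 footnote 3 ends expedited reports at month 6, while Section 10.4 requires related late SAEs to be reported with no end date

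*Combined protocol and SAP*

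**What the plan says.** Section 18.1 lists the forms due during Active Monitoring. In its observation column, the ADR/AER entry begins "At each occurrence (see Section 10.0" and carries footnote 3. The routine form is labelled "Nadir/Adverse Event (Cycles 1 & 2 Only" and its observation entry carries the same footnote. Footnote 3 reads: "AE form and expedited reports needed for Cycle 1 (treatment – months 0-3) and Cycle 2 (first cycle of observation – months 3-6) only".

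Section 10 sets the reporting duties themselves:

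- **10.4 footnote 1.** SAEs that arise more than 30 days after the last administration, and are possibly, probably or definitely related, need an expedited report. Grades 4 and 5 need notice in 24 hours and a full report within 3 further days. Grade 3, and Grade 2 with hospitalization, need a report in 7 days. No end date is given.
- **Manufacturer notice, after the 10.4 table.** Any event that meets an SAE criterion must be notified within 24 hours of first knowledge. No end date is given.
- **10.41.** "Any protocol specific reporting procedures MUST BE SPECIFIED BELOW and will supercede the standard Expedited Adverse Event Reporting Requirements". The table that follows lists five blood-count terms and no time limit.
- **10.6132.** A death more than 30 days after the last study treatment "that is felt to be at least possibly treatment related must also be submitted as a Grade 5 AE". No end date is given.
- **10.53, last bullet.** "Any malignancy possibly related to cancer treatment (including AML/MDS) should also be reported via the routine reporting mechanisms outlined in each protocol".
- **10.62.** The Forms Packet is to be consulted "regarding the submission of late occurring AEs following completion of the Active Monitoring Phase".

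**The concern.** The ADR/AER entry refers the site to Section 10 for every event and then, through its footnote, stops that duty at month 6. A coordinator working from the submission table could reasonably conclude that a related SAE at month 14 needs no expedited report. Section 10.4 requires one within 24 hours or 7 days, depending on grade.

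At stake is complete reporting of late related SAEs, including related AML or MDS where it meets the SAE definition (Section 15.27 lists both as Zevalin toxicities), and of late related deaths. These are safety-reporting duties. The complete response comparison at 6 months does not depend on them.

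**Working it through.** The plan states no figure to reproduce. The check compares the rules and then measures the period in conflict.

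**1. The rules after month 6, for a patient still in observation**

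| Event | Section 10 | 18.1 footnote 3 |
|---|---|---|
| Related SAE | Expedited report, no end date (10.4 footnote 1) | Expedited reports stop at month 6 |
| Any SAE, notice to manufacturer | Within 24 hours, no end date | Not mentioned separately |
| Related death | Submit as a Grade 5 AE, no end date (10.6132) | AE form stops at month 6 |
| Possibly related malignancy | Routine reporting as well (10.53) | AE form stops at month 6 |

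The first row concerns the expedited half of the footnote. The last two concern the AE-form half, because 10.6132 and the last bullet of 10.53 govern routine reporting.

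**2. Is footnote 3 an authorised exception?** The notes to 10.4 place exceptions to expedited reporting in 10.41, and 10.41 says they must be written there. Its five entries are anemia and decreased white cells, lymphocytes, neutrophils and platelets. None carries a time limit, so by the plan's own rule footnote 3 is not an exception.

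**3. Where does month 6 come from?** It is not the 30-day window of 10.4. That window closes on day 8 + 30 = 38 in Arm B and day 22 + 30 = 52 in Arm A, whereas month 6 is 6 × 365.25/12 = day 182.6. It does match the Test Schedule (Section 4.0), where adverse event assessment is marked at baseline, month 3 and month 6 and, in the extracted table, at no later visit. The footnote therefore reads naturally as the end of scheduled AE collection, with expedited reports swept in.

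**4. Does another passage cover the period?** 10.62 applies only after Active Monitoring is complete. The note to 3.19f defines Active Monitoring as active treatment plus observation, and the Test Schedule places the visits to month 60 under it. A patient in observation at months 6 to 60 is therefore outside 10.62, and also outside the Event Monitoring table of 18.1, which starts when observation ends (13.4, 13.5).

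**5. Length of the conflict.** Visits from day 1 of treatment (13.2) are at months 3 and 6, then 9, 12, 18, 24, 30, 36, 48 and 60.

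- Visits after the limit: 8 of 10.
- Months after the limit: 60 − 6 = 54 of 60, or 54/60 = 90%.

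This is a maximum. Progression, new lymphoma treatment, refusal or failure to return moves a patient to event monitoring sooner (13.4). The figures measure calendar time, not events; the documents give no event rate after month 6.

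**The case against.** The best defence is that the plan has several safeguards. Section 10.4 tells investigators to report any SAE to the sponsor immediately, the manufacturer notice has no time limit, and the disputed cell itself points to Section 10. A site would have to set all of that aside to miss a report. This makes omission less likely, but these statements are one side of the contradiction and do not resolve it: the footnote on the same cell says *only*. The Forms Packet and the Evaluation/Observation form are not among the documents and might capture some events, but an unseen form cannot cancel that word.

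The defence is right that the month-6 limit has a visible source in the Test Schedule. A reader might infer that routine AE collection should run to month 60. The documents do not support that: the Test Schedule and the label of the routine form agree on the limit, which looks deliberate.

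Two other stronger readings also fail:

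- **A gap lasting to year 10.** After observation ends, 10.62 and the Event Monitoring table apply, and that table records deaths and new primaries. The conflict shown here ends at month 60 at the latest.
- **The late MDS case in Section 1.2 as an example of what would be missed.** It came at eight years, after a different radioimmunotherapy agent and further chemotherapy. By that time a patient in this trial would be in event monitoring.

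Finally, 10.52 and the second bullet of 10.53 are worded for agents under an IND/IDE, whereas the 10.4 table is for a non-IND/IDE trial. This point therefore rests on 10.4 footnote 1 for expedited reports, and on 10.6132 and the last bullet of 10.53 for routine ones.

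**Conclusion.** The contradiction is real and stands in the current text. Footnote 3 of 18.1 ends expedited reports at month 6. Section 10.4 footnote 1 and the manufacturer notice do not, and 10.41 contains no exception that would permit it. The AE-form half of the footnote conflicts in the same way with 10.6132, and it leaves possibly related malignancies under 10.53 without a named form. The period affected is observation from month 6 to month 60, at most 54 of 60 months and 8 of 10 post-baseline visits.

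The practical yield is probably small. Section 1.2 regards the risk of MDS in patients never given chemotherapy as negligible, and the expectation of few late events rests on that judgement, not on a stated rate. The primary endpoint is unaffected. The point still merits correction because the duty is mandatory and the edit is short. The conclusion assumes that the Test Schedule columns were extracted correctly and that no unseen form overrides the footnote.

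**What to change.** Reconcile Section 18.1 with Section 10:

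1. Remove expedited reports from footnote 3, and remove the footnote marker from the ADR/AER entry in the observation column, so that the entry follows Section 10 at each occurrence throughout observation.
2. Keep the Cycles 1-2 limit on the Nadir/Adverse Event form for routine scheduled collection, in line with the Test Schedule.
3. Add a sentence that this limit does not apply to late related deaths under 10.6132 or possibly related malignancies under 10.53, which are submitted on that form, or on a named equivalent, when they occur.

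The cost is an edited footnote, one deleted marker and one added sentence. No visits are added, since patients are already seen to month 60. The downside is a few more forms.
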